6.5 Prohibited medication and rescue medication

Prohibited medications are defined in the Protocol (Section 7.8.2).

Rescue medication will be allowed for some subjects evaluated at weeks 16, 24, and 36. Further details are defined in the Protocol (Section 5.1.4). The number and percentage of subjects who used rescue medication will be summarized and listed.

The SS and FAS will be used for both summary tables and the RS will be used for the listings.

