### 5.1.3 Dose-Blind Period

After the 12-week Double-Blind Period, subjects will enter the 36-week Dose-Blind Period. At the Week 12 Visit, subjects will be allocated to bimekizumab treatment regimens as follows:

- Subjects in the placebo group will be rerandomized 1:1 to bimekizumab 160mg or bimekizumab 320mg Q4W
- Subjects in the bimekizumab 16mg dose group will be rerandomized 1:1 to bimekizumab 160mg or bimekizumab 320mg Q4W
- Subjects in the bimekizumab 160mg dose group will continue to receive bimekizumab 160mg Q4W

- Subjects in the bimekizumab 320mg dose group will continue to receive bimekizumab 320mg Q4W
- Subjects in the bimekizumab 320mg (loading)/160mg dose group will continue to receive bimekizumab 160mg Q4W

The assessments at each Dose-Blind Period Visit are presented in [Table 5–1](#).

During the 36-week Dose-Blind Period, subjects will be evaluated for inadequate response to treatment at defined time points. Subjects who do not show an improvement in tender and swollen joint count will be eligible to receive rescue therapy as defined in [Section 5.1.4](#).

At the completion of the Dose-Blind Period, Investigators should discuss treatment options with the subject. Subjects will be given the opportunity to enter an extension study at [Week 48](#), provided they do not qualify for rescue therapy as outlined in [Section 5.1.4](#).

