### 7.8.1 Permitted concomitant treatments (medications and therapies)

No medication increases or additions are permitted for medications taken for PsA until after the Week 16 visit assessments. However, a decrease in dose or dosing frequency of any agent is permitted for reasons of intolerance/AEs/side-effects at any time.

At Week 16, Week 24, and Week 36 of the Dose-blind Period, subjects will be evaluated for their response to treatment to determine eligibility for rescue therapy.

Subjects who have shown <10% improvement from Baseline in TJC and SJC will be eligible for rescue therapy. Rescue therapy for eligible subjects will be at the Investigator's discretion, with the following options:

- Nonsteroidal anti-inflammatory drugs, DMARDs (MTX, sulfasalazine, LEF, apremilast), and/or joint injections may be given as rescue therapy if deemed appropriate by the Investigator as outlined below. Subjects may receive these add-on therapies while continuing to receive their randomized dose of bimekizumab.
  - For subjects taking NSAID/COX-2 inhibitors at Baseline or at Week 16, Week 24, or Week 36, a change can be made to a different NSAID/COX-2. Changes from an NSAID to a COX-2 or from a COX-2 to an NSAID are permitted up to the maximum approved or tolerated dose, whichever is lower. Only 1 NSAID/COX-2 may be taken at a given time.
  - For subjects not taking NSAID/COX-2 inhibitors at Baseline, Week 16, Week 24, or Week 36, either a NSAID or COX-2 inhibitor can be initiated, up to the maximum approved or tolerated dose, whichever is lower. Only 1 NSAID/COX-2 may be taken at a given time.
  - Methotrexate may be added or increased to a maximum dose of 25mg/week, or the maximum tolerated dose, whichever is lower. The route of administration may be changed from oral to sc.
  - Sulfasalazine may be given up to a maximum dose of 3g/day, or the maximum tolerated dose, whichever is lower.
  - Leflunomide may be given at a maximum dose of 20mg/day (or an average of 20mg/day if not dosed daily), or the maximum tolerated dose, whichever is lower.
  - Apremilast may be given at a maximum dose of 30mg twice daily, or the maximum tolerated dose, whichever is lower.
  - Combination DMARDs are allowed except that LEF and MTX may not be given together.
    - One joint may be injected at or after the Week 16, Week 24, and Week 36 Visit; however, the same joint should not be injected more than once during the study.

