- Bimekizumab 160mg with loading dose 320mg
- Bimekizumab 320mg

The general principle is to go from the lowest to highest dose when moving from left to right. Tables may also include columns for all subjects or all subjects on bimekizumab. An overview of the treatment group assignment is available in [Section 12.3](#).

Selected tables which are specified in the TFL shells will only use data from the Dose-Blind Period. For listings and the selected tables, the label and order of treatment groups will be presented as follows:

- Placebo to bimekizumab 160mg at Week 12
- Placebo to bimekizumab 320mg at Week 12
- Bimekizumab 16mg to bimekizumab 160mg at Week 12
- Bimekizumab 16mg to bimekizumab 320mg at Week 12
- Bimekizumab 160mg with loading dose 320mg to bimekizumab 160mg at Week 12
- Bimekizumab 160mg
- Bimekizumab 320mg

The abbreviation for bimekizumab is BKZ and will be used in tables and listings headers. In the TFLs subjects on bimekizumab 160mg with loading dose 320mg will be displayed as “BKZ 160mg w/LD”. All subjects on bimekizumab will be labeled as “All BKZ” in the TFLs.

A complete set of data listings containing all documented data and all derived data (eg, change from Baseline) will be generated.

Unless otherwise stated, listings will be sorted by treatment, subject number within each treatment group (not randomization number), variable (if applicable) and visit (if applicable; including timing relative to dosing if applicable). For listings including nonrandomized subjects, the nonrandomized subjects will be shown first in the listing, ordered by subject number. All listings will include repeat and unscheduled measurements; such measurements will appear in chronological order together with the scheduled visits, ie, a repeated measurement will appear directly after the visit and time relative to dosing for which the repeat measurement was performed. In all the listings dates will be presented in the format 'YYYY-MM-DD' and times will be presented in 24h clock format as 'hh:mm'.

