3.7 Treatment assignment and treatment groups

It is expected that subjects receive treatment as randomized and hence safety analyses will be based on the SS, as randomized. However, if after unblinding it is determined that subjects randomized to placebo received bimekizumab at any time, then for safety analyses these subjects will be reallocated to the appropriate bimekizumab treatment group. Subjects randomized to bimekizumab will only be reallocated to the placebo treatment group if they did not receive bimekizumab at any time during the study.

Depending on the analysis sets, subjects will be summarized and listed based on the actual received treatment or according to the randomization which will be considered as planned treatment:

- All subjects screened/ES: planned treatment
- RS: planned treatment
- SS: actual treatment
- FAS: planned treatment
- PPS: planned treatment
- PK-PPS: actual treatment
- PD-PPS: actual treatment
- DBS: planned treatment (demographics, baseline characteristics, and efficacy analyses) or actual treatment
- ESS: planned treatment
- DBRS: planned treatment
- cESS: planned treatment
- cDBRS: planned treatment

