12.3 Treatment group assignment for tables and figures

Table 12–3 displays the treatment group labels for each data type. This overview clarifies what kind of treatment groups will be used for producing the tables and figures separated between the different table types.

Table 12–3: Treatment group assignment for tables and figures

	Placebo	BKZ 16mg, BKZ 160mg w/LD / BKZ 160mg/ BKZ 320mg	All BKZ	All subjects
Subject disposition	X	X		X
Important protocol deviation	X	X		X
Demographics/Lifestyle	X	X		X
Ankylosing spondylitis history	X	X		X
Baseline characteristics	X	X		X
Tuberculosis testing	X	X		X
Previous and ongoing medical history	X	X		X
Prior and concomitant medication	X	X		X

Table 12–3: Treatment group assignment for tables and figures

	Placebo	BKZ 16mg, BKZ 160mg w/LD / BKZ 160mg/ BKZ 320mg	All BKZ	All subjects
Rescue and prohibited medication	X	X		X
Bimekizumab compliance	X	X	X	
Extent of exposure	X	X	X	
Efficacy analysis	X	X		
Plasma/Bimekizumab concentration	X	X		
Pharmacokinetic variables/Biomarker data/AbAb	X	X		
AEs	X	X	X	
Safety laboratory tests	X	X	X	
Vital signs/Body weight/ECG/ Physical examination	X	X	X	
eC-SSRS	X	X	X	

BKZ=bimekizumab; eC-SSRS= Electronic Columbia-Suicide Severity Rating Scale; LD=loading dose.

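### The rescue-use table is specified on the SS and FAS with Placebo and 16mg columns, although rescue can begin only at Week 16, after both arms have switched to 160mg or 320mg

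*SAP*

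**What the plan says.** **When rescue can occur.** SAP 6.5 states: "Rescue medication will be allowed for some subjects evaluated at weeks 16, 24, and 36". Protocol 7.8.1 closes off anything earlier: "No medication increases or additions are permitted for medications taken for PsA until after the Week 16 visit assessments".

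**What subjects are taking by then.** Protocol 5.1.3 provides that "Subjects in the placebo group will be rerandomized 1:1 to bimekizumab 160mg or bimekizumab 320mg Q4W", and gives the 16mg arm the same 1:1 split. SAP 2.3 places the first Dose-Blind dose at Week 12. The other three arms stay on 160mg or 320mg.

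**How rescue is to be tabulated.** SAP 6.5 says "The number and percentage of subjects who used rescue medication will be summarized and listed", and then "The SS and FAS will be used for both summary tables and the RS will be used for the listings". The DBS is not named. In SAP Table 12-3 the row "Rescue and prohibited medication" is marked for Placebo, for the joint cell covering 16mg, 160mg with loading dose, 160mg and 320mg, and for All subjects. SAP 3.7 gives "FAS: planned treatment" and assigns the SS by actual treatment.

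**What else the SAP has available.** SAP 3.1 defines seven sequence labels, beginning with "Placebo to bimekizumab 160mg at Week 12", for listings and for selected Dose-Blind tables that are identified only in the table shells.

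**The concern.** A rescue table is read as showing how often each treatment needed supplementing. Here, a protocol-permitted rescue counted under Placebo or 16mg, when subjects are shown by planned treatment, was taken on 160mg or 320mg. Those two columns cannot describe placebo or 16mg, and each blends the two continuing doses. A reader could take the table for a drug-versus-placebo comparison that the design does not contain, and could not obtain rescue use by current dose from it.

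Elsewhere the SAP deals with the switch explicitly. Compliance for a switcher counts only time on the new dose (SAP 7), exposure is split at the switch (SAP 10.1), and adverse events follow the treatment in use at onset (SAP 10.2). SAP 3.6 makes the DBS the main set for Dose-Blind analyses as the least biased choice. SAP 6.5 has no comparable rule.

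**Working it through.** **Inputs.** 200 subjects, 40 per arm (SAP 2.4); 1:1 rerandomization of the placebo and 16mg arms at Week 12 (Protocol 5.1.3); rescue evaluations at Weeks 16, 24 and 36 (SAP 6.5). The documents give no rescue or dropout rates, so those used below are assumptions.

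**Plan's own figure.** 5 arms × 40 = 200, as stated.

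**Step 1. Dose in use at the rescue visits, planned numbers before dropout.**

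| Column in Table 12-3 | Randomized | On 160mg | On 320mg |
|---|---|---|---|
| Placebo | 40 | 20 | 20 |
| 16mg | 40 | 20 | 20 |
| 160mg | 40 | 40 | 0 |
| 160mg with loading dose | 40 | 40 | 0 |
| 320mg | 40 | 0 | 40 |
| Total | 200 | 120 | 80 |

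Nobody is on placebo or 16mg. Shown under one of those two headings are:
- of those on 160mg, 20 + 20 = 40 of 120 (33%);
- of those on 320mg, 20 + 20 = 40 of 80 (50%);
- overall, 80 of 200 (40%).

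**Step 2. Effect on the table.** Assume that the chance of rescue depends only on current dose, at 10% on 160mg and 5% on 320mg.
- Users: 120 × 0.10 + 80 × 0.05 = 12 + 4 = 16.
- Placebo column: 20 × 0.10 + 20 × 0.05 = 3, shown as 3/40 = 7.5%.
- 16mg column: the same, 3/40 = 7.5%.
- The two 160mg columns together: 80 × 0.10 = 8. The 320mg column: 40 × 0.05 = 2.
- Share of users under a treatment not being taken: (3 + 3)/16 = 37.5%.

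With 5% on both doses the share is (2 + 2)/10 = 40%. With 20% and 10%, or 30% and 15%, it is again 37.5%.

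**Step 3. Denominators.** The SS and FAS keep subjects who left before Week 16. If a fraction d leaves early, a rate r among those remaining is shown as r × (1 − d). For r = 10% and d from 0 to 15%, the table shows 10% down to 10% × 0.85 = 8.5%.

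**The case against.** The strongest reply is that Table 12-3 is a generic grid and does not settle the layout. Its compliance, exposure and adverse-event rows also mark Placebo, yet SAP 7, 10.1 and 10.2 present the longer period by bimekizumab group only. SAP 3.1 leaves the list of tables carrying the seven sequence labels to shells that are not among the documents, and rescue, which exists only in the Dose-Blind Period, is a natural candidate. This stands in part: the shells could resolve the matter. But the other outputs depart from the grid because their own sections say so, whereas SAP 6.5 names the SS and FAS and says nothing further.

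Several stronger readings are tempting, and the documents do not support them.
- **That misattribution is established for both sets.** It is firm for the FAS, which is by planned treatment. The SS is by actual treatment, and no time-of-use rule is given for this table.
- **That rescue directly measures inadequate response.** Protocol 5.1.4 leaves rescue for eligible subjects to the Investigator's discretion, and it is not among the efficacy variables. The response criterion is the joint-count rule that sets eligibility.
- **That the Placebo and 16mg columns should be removed from the row.** The row also covers prohibited medication, which can be used during the Double-Blind Period, so those columns are valid for that output.
- **That the percentages are seriously understated.** Step 3 shows a small effect under plausible early dropout, and reporting on all treated subjects is conventional.

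The information is also not lost. SAP 6.5 requires a rescue listing, and SAP 3.1 gives listings the sequence labels. The cESS (SAP 3.6.11) identifies subjects who met the rule and received rescue.

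**Conclusion.** The point holds as a specification fault in one descriptive table. SAP 6.5 and Table 12-3, read with SAP 3.7, would place rescue in up to 80 of 200 planned subjects under a treatment not being taken. That count assumes planned arm sizes, an exact 1:1 split and no dropout. It is a count of subjects whose rescue, if any, would be shown in the wrong place, not of rescue events. The share of rescue users affected was 37.5% to 40% over the assumed rates.

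The 120 subjects randomized to 160mg, 160mg with loading dose or 320mg appear under the right dose. The Week 12 primary and secondary analyses are not touched. The change should still be made, because the existing text fixes a set and columns that do not suit the data, and the SAP already contains what is needed to correct it.

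**What to change.** In SAP 6.5, summarise rescue use on the DBS by the seven treatment sequences of SAP 3.1, with totals for 160mg and 320mg. For Weeks 16, 24 and 36, give the number evaluated and the number meeting the protocol's eligibility rule. The number evaluated is needed even on the DBS, which still includes anyone dosed at Week 12 who leaves before Week 16.

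Split the Table 12-3 row in two: rescue with the sequence columns, and any prohibited-medication output with its present Placebo and Double-Blind columns. If the shells already lay out rescue this way, SAP 6.5 should say so.

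The cost is a short SAP wording change and one re-specified table. No new data collection is involved.

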7 MEASUREMENTS OF TREATMENT COMPLIANCE

Compliance will be summarized as the number of doses received relative to the number of doses scheduled:

$$\text{Percent compliance} = 100 * \frac{\text{Number of doses received}}{\text{Number of doses expected}} \quad (8)$$

where the total number of expected doses is derived relative to when the subject finishes treatment. If a subject completes treatment 12 doses are expected (Baseline and every 4th week

afterwards until Week 44). If a subject discontinues early, then the number of expected doses is based on the time of early discontinuation relative to the dosing visits. If a dose is not completely given at a specific visit (eg, subject only received one injection instead of the two planned injections), then the subject will be considered to have no compliance for the visit. In the formula above it will be counted as no dose received at this visit.

A summary of percent treatment compliance categorized as $\leq 80\%$ and $> 80\%$ will be provided by treatment group for the overall treatment period as well as for Double-Blind treatment period. For the Double-Blind treatment period compliance will refer to the first 12 weeks and will be presented by treatment received at baseline. For the overall treatment period, the compliance will be calculated for the following three groups: bimekizumab 160mg and 160mg with loading dose, bimekizumab 320mg, and all bimekizumab. Treatment compliance for the bimekizumab 160mg and 160mg with loading dose group will be calculated for the time the subject receives 160mg or 160mg with loading dose, eg for a subject who switches from Placebo or bimekizumab 16mg to bimekizumab 160mg at Week 12, the compliance will only be calculated for the time the subject receives bimekizumab 160mg. The same approach will be done for bimekizumab 320mg. The all bimekizumab group will consist of all the doses of bimekizumab including bimekizumab 16mg, and will only exclude the time subjects receive Placebo.

A by-subject listing of treatment compliance will be provided, presenting, percent compliance and numbers of expected and received doses for the Double-Blind Period and for treatment with any dose of bimekizumab.

8 EFFICACY ANALYSES

8.1 Statistical analysis of the primary efficacy variable

8.1.1 Derivations of primary ACR score and response

ACR20/50/70 response represents at least 20%, 50%, or 70% respective improvement from Baseline for each of the following:

- TJC (based on 78 joints)
- SJC (based on 76 joints)
- At least 3 of the 5 remaining core set measures
 - Disease activity as assessed by PGADA
 - Disease activity as assessed by PhGADA
 - Pain as assessed by PtAAP
 - Physical function as assessed by the HAQ-DI
 - Acute phase response as assessed by the hs-CRP

For all non-missed visits, if any of the component scores are missing, then those scores will be considered as not having met the criteria for improvement for the respective component. For component scores with a Baseline value of 0, the percentage improvement is not calculable and is treated as missing. However, if ACR20, ACR50, or ACR70 response is used as the primary endpoint in a study, consideration should be given to requiring a value > 0 for each of the component endpoints in order to enter the study. For component scores with a Baseline value > 0

and a post-Baseline value of 0, percentage improvement will be calculated as for any other non-missing data.

Missing items for TJC, SJC, and HAQ-DI will be handled as described in [Section 8.1.1.1](#) and [Section 8.1.1.5](#).

8.1.1.1 Tender joint count (TJC) and swollen joint count (SJC)

8.1.1.1.1 78/76 joint evaluation for ACR response

The Principal Investigator, another delegated physician, or an appropriately qualified medical professional (based on local requirements) who has had documented training on how to perform these assessments correctly assesses the following joints for tenderness: the distal interphalangeal, proximal interphalangeal and metacarpophalangeal joints of the hands, and metatarsophalangeal joints of the feet, the carpometacarpal and wrist joints (counted separately), the elbows, shoulders, acromioclavicular, sternoclavicular, hip, knee, talo-tibial, and midtarsal joints. All of these except for the hips are assessed for swelling.

Artificial and ankylosed joints, as well as missing joints (ie, amputated joints), are excluded from both tenderness and swelling assessments.

One dactylitic digit is to be counted as 1 swollen joint (instead of counting as 3 in the finger or 2 in the toe).

[Table 8–1](#) summarizes the swelling and tenderness grading criteria.

Table 8–1: Swelling and tenderness grading

The tender joint counts (TJC) and swollen joint counts (SJC) are weighted joint counts. If there are missing observations in the tender or swollen joint assessments, then the remaining observations will be assessed and weighted by the number of the assessed joints (AJ):

$$SJC = n * \sum_{i=1}^n SJ / \sum_{i=1}^n AJ \tag{9}$$

$$TJC = n * \sum_{i=1}^n TJ / \sum_{i=1}^n AJ \tag{10}$$

where n is the number of total joints. If a joint is missing at Baseline, then that joint is set to missing throughout the study. If more than 50% of the tender joint assessments or 50% of the

swollen joint assessments are missing at the time of a given assessment, then no imputation will be done and the total TJC or SJC will be set to missing for that visit.

Injected joints will be counted as swollen and tender from the date of injection up to 52 weeks after injection, ie, swelling and tenderness grading is 1.

8.1.1.1.2 28 joint evaluation for determination of DAS28(CRP)

The following 28 joints will be used for calculation of the DAS28(CRP).

- Upper extremity (26)-bilateral shoulders, elbows, wrists (includes radiocarpal, and carpal and carpometacarpal bones considered as a single unit), MCP I, II, III, IV, and V, thumb interphalangeals (IP), PIP II, III, IV, and V
- Lower extremity (2)-knees

Injected joints will be counted as swollen and tender from the date of injection up to 52 weeks after injection, ie, swelling and tenderness grading is 1.

8.1.1.2 Patient's Global Assessment of Disease Activity (PGADA)

Subjects will score their Global Assessment of Disease Activity using a visual analog scale (VAS) where 0 is "very good, no symptoms" and 100 is "very poor, severe symptoms". The subject should be asked to consider both joint and skin components in their response to this question.

8.1.1.3 Physician's Global Assessment of Disease Activity (PhGADA)

The Investigator will assess the overall status of the subject with respect to their PsA signs and symptoms and functional capacity (considering both joint and skin components) using a numerical rating scale (NRS) where 0 is "very good, asymptomatic and no limitation of normal activities" and 100 is "very poor, very severe symptoms which are intolerable and inability to carry out all normal activities".

8.1.1.4 Patient's Assessment of Arthritis Pain (PtAAP)

The PtAAP VAS is part of the ACR core set of measures in arthritis (Felson et al, 1993). Subjects will assess their arthritis pain using a VAS where 0 is "no pain" and 100 is "most severe pain".

[figure not shown]
8.1.1.5 Health Assessment Questionnaire-Disability Index (HAQ-DI) score

The HAQ-DI contains 20 items divided into 8 domains that measure: dressing and grooming (2 items), arising (2 items), eating (3 items), walking (2 items), hygiene (3 items), reach (2 items), grip (3 items), and common daily activities (3 items). The questionnaire is available in the Appendix [Section 12.5](#). Subjects are required to indicate the degree of difficulty they have experienced in each domain in the past week on a 4-point scale that ranges from 0 (without difficulty) to 3 (unable to do). The highest score in each category is then summed (0 to 24) and divided by the number of categories scored to give a score that ranges from 0 to 3.

Any individual score of less than 2 is adjusted to 2 if the activity requires assistance from another individual or the use of an assistive device. If the category score is already a 2, and a device related to that category is used, or help from another person is provided for the category, the

score for that category remains 2. The following list details how each aid and device is associated with the category scores (Table 8–2):

Table 8–2: Aid or Device associated with HAQ-DI domain

The table content is redacted with a solid black box. A diagonal watermark 'This document cannot be used for regulatory submissions thereof.' is visible across the page.

If all questions within a given category are unanswered, no score will be provided for that category (this rule applies even if aids and devices are non-missing). The HAQ-DI will be calculated by dividing the sum of the category scores by the number of categories with at least 1 question answered. If fewer than 6 categories have responses, no disability score will be calculated. A lower HAQ disability score indicates an improvement in function.

